Despite recent prioritization of personalized medicine, there is insufficient information to guide tailored treatment decision-making for fatigue management in MS. For example, although data from other chronic health conditions such as major depressive disorder and fibromyalgia suggest that combination therapies of both pharmacological and behavioral approaches can have synergistic effects and offer the best chance of long-term success for symptom management, only single-treatment modalities have been studied for MS fatigue. Furthermore, prior trials of treatments for MS-fatigue have not taken into account specific MS subpopulations who may, by virtue of common comorbidities, respond better to one particular treatment or combination of treatments. Finally, existing trials of some of the most commonly used treatments for MS fatigue have relied on measures that do not fully reflect the patient experience with this symptom. Consequently, clinicians have little evidence to determine whether a specific monotherapy or combination therapy is indicated for a particular patient. Specifically, three major research gaps have contributed to the current decisional uncertainty regarding the approach to fatigue treatment in MS: (1) lack of pragmatic, comparative effectiveness trials, including trials of combination therapies, for two of the most commonly used non-pharmacologic and pharmacologic treatments in clinical practice; (2) lack of assessment of common treatment effect modifiers associated with MS that contribute to fatigue (depression, sleep, and progressive MS/disability severity); and (3) lack of novel, reliable patient-centered fatigue outcome measures.

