9.0 DATA ANALYSIS/STATISTICAL METHODS

9.1 Sample Size Determination

Estimates are derived from recent data from the study team, and published interventional studies of modafinil and CBT monotherapy. The primary sample size determinant for this study is Aim 1.

For Aim 1, we have chosen the Modified Fatigue Impact Score (MFIS) as the primary outcome variable of interest. The MFIS has been validated in MS patients, is frequently used in MS clinical studies as a reliable measure of fatigue, and is sensitive to changes in intervention. The primary outcome measure will be the mean within-subject difference between baseline and 12-week MFIS values (delta-MFIS), compared between groups. Based on a power analysis of 2-sample means (combined monotherapy groups vs. combination therapy, group weights 2:1), with a 2-sided alpha of 0.05 and standard deviation of 12, a sample size of n=300 subjects will provide 92% power to detect a delta-MFIS of 5 between the monotherapy and combination treatment arms (see power curve); this difference is similar to group differences found in previous fatigue trials.

For Aim 2 analyses, using fatigue outcomes as the dependent variables (in separate models) a multiple linear regression power analysis was performed assuming a full model consisting of up to 11 possible predictor variables: treatment group, presence of sleep disturbance (yes/no), depression severity (PHQ-9 Score), disability severity (EDSS score), 3 interaction terms (treatment*sleep, treatment*depression, and treatment*disability), baseline fatigue level, anxiety, pain, and exercise. A similar model will also be constructed using MS subtype and treatment*MS subtype interaction term, (in place of EDSS) to determine if subtype conveys differences in fatigue outcome separate from pure disability measures. Based on a sample size of n=300, we will have 85% power to detect an R-square difference of 0.04 for the interaction term of interest, assuming the R-squared explained by the adjustment variables is at least 0.3.

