For Aim 3, using treatment adherence as the dependent variable (continuous outcome), a multiple linear regression power analysis was performed assuming a full model consisting of up to 8 possible predictor variables: treatment group (independent variable of interest), age, gender, EDSS score, baseline fatigue level, baseline activity level, presence of sleep disturbance (yes/no), and depression severity (PHQ-9 Score). Based on a sample size of n=300, we will have 95% power to detect an R-square difference of 0.03 for the test predictor of interest, assuming the R-squared explained by the adjustment variables is at least 0.3.

9.2 Analysis of Study Aims:

Aim 1: Compare the effectiveness of 3 therapies: CBT monotherapy, modafinil monotherapy, and CBT+modafinil combination therapy on patient-reported fatigue impact (primary outcome), fatigue intensity, and fatigability among fatigued individuals with MS. The primary outcome measure will be the mean difference in Modified Fatigue Impact Scale (MFIS) score between 12 weeks and baseline (delta-MFIS), compared between treatment groups. A repeated measures mixed effects model will be applied. The mean difference will also be adjusted for baseline covariates: age, gender, anxiety, pain, and exercise, which were included as covariates based on their established association between fatigue and/or activity in MS. Additional secondary analyses will also evaluate treatment effect on EMA outcome measures of fatigue impact, fatigue intensity, and fatigability.

Aim 2: Test whether depression, sleep disturbances, or MS disability level modify comparative treatment responsiveness across treatment arms in terms of fatigue impact (HTE analyses). Treatment group effect on fatigue impact scores, fatigue intensity, and fatigability among select subgroups, including those with clinically significant depression, progressive MS subtype and higher EDSS scores, and confirmed/suspected sleep disorders not related to poor sleep hygiene, will be evaluated with interaction terms in mixed effects models as above.

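### The supplementary MS-subtype model drops EDSS, so it cannot answer its stated question of whether subtype matters separately from disability

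*Combined protocol and SAP*

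**What the plan says.** Section 9.1 sets out the main Aim 2 model. Beside treatment, sleep disturbance and depression it contains "disability severity (EDSS score), 3 interaction terms (treatment*sleep, treatment*depression, and treatment*disability), baseline fatigue level, anxiety, pain, and exercise". EDSS is the only disability measure in that list, and treatment*disability is the only interaction involving disability.

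The next sentence adds a further model, in which MS subtype and its treatment interaction are entered "in place of EDSS) to determine if subtype conveys differences in fatigue outcome separate from pure disability measures". The substitution and the purpose it is meant to serve thus stand in the same sentence.

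Elsewhere the protocol treats the two characteristics as neighbours. Section 1.2 names "progressive MS/disability severity" as one of the modifier domains that earlier trials neglected. Section 9.2, Aim 2, lists "progressive MS subtype and higher EDSS scores" among the subgroups to be tested with interaction terms. No section specifies a model that holds both subtype and EDSS: the Aim 1 covariates in 9.2 include neither, and the Aim 3 adherence model has EDSS but not subtype.

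**The concern.** An effect of subtype apart from disability has to be estimated with disability held constant. The model planned for that purpose takes out the only disability measure. What remains (sleep, depression, baseline fatigue, anxiety, pain, exercise) does not measure disability, and the only other interactions, with sleep and depression, are poor stand-ins for treatment*EDSS.

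Two conditions turn this into bias: subtype and EDSS must be correlated, and EDSS must relate to the outcome or to treatment response after the other covariates. The protocol assumes something close to the first by pairing the two as one domain, and Aim 2 tests the second. So if the trial's own hypothesis about disability is right, the subtype model is confounded.

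At stake is a statement that progressive MS responds differently for reasons other than disability, in a trial meant to inform which patients should receive which treatment. The planned model could not support that statement.

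**Working it through.** **1. The plan's own Aim 2 figure.** The section states: "Based on a sample size of n=300, we will have 85% power to detect an R-square difference of 0.04", with adjustment variables explaining at least 0.3. Using f² = ΔR²/(1 − R² of the full model) = 0.04/(1 − 0.34) = 0.0606 and λ = 300 × 0.0606 = 18.2, with 11 predictors and alpha 0.05 (stated for Aim 1, assumed here), power is 98.9% for a 1-df interaction and 97.4% for 2 df. The stated 85% is not reproduced, but it errs on the cautious side. It is a separate matter and this point does not depend on it.

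**2. What the subtype model estimates.** Write the change in MFIS as bE + g(T×E) + error. E is EDSS, T is combination therapy, and subtype S has no effect of its own. Let EDSS be Δ points higher on average in progressive participants. A model with T, S and T×S but no EDSS then has these expected coefficients:

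- subtype: b × Δ
- treatment*subtype: g × Δ

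Both are zero if Δ = 0. The first is also zero if b = 0, and the second if g = 0.

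**3. Inputs.** From section 9.1: n=300, a 2:1 split of pooled monotherapy to combination (200 v 100), SD 12, design difference 5 MFIS points. Assumed, because the documents are silent: 30% progressive, EDSS SD 1.5 within subtype, Δ = 1.5 to 3, g = 0 to 2 MFIS points per EDSS point, and b = 1 to 1.5.

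**4. False treatment*subtype interaction, Δ = 2.** The standard error is about 12 × √[1/(100 × 0.21) + 1/(200 × 0.21)] = 12 × 0.267 = 3.21, where 0.21 = 0.3 × 0.7.

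| g per EDSS point | Spurious effect gΔ | Rejection by formula | Rejection by simulation |
|---|---|---|---|
| 0 | 0 | 5% | about 5% |
| 0.5 | 1 | 6% | about 6% |
| 1 | 2 | 10% | about 10% |
| 2 | 4 | 24% | about 23% |

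The formula is P(|Z + gΔ/3.21| > 1.96). Simulated rates are slightly lower at large g because omitted EDSS also adds to the residual variance. Independent runs of this set-up put the first two rows at 5-7%.

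**5. Spurious subtype main effect, Δ = 2.** It is bΔ = 2 points for b = 1 and 3 points for b = 1.5, rejected in about 18% and 33% of runs. This is a difference in outcome by subtype, not heterogeneity of treatment effect.

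**6. A second parameterisation.** With 25% progressive, and main and modifying EDSS effects of 3 MFIS points per SD, subtype-EDSS correlations of 0.21, 0.40, 0.54 and 0.65 give spurious interactions of 1.6, 2.8, 3.7 and 4.5 points, rejected in 8%, 13%, 20% and 24% of runs. At zero correlation, or with no EDSS effect, there is no bias.

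**7. Joint model.** With EDSS and treatment*EDSS both kept, the spurious effects average about zero and rejection is 4-6% in both set-ups. Adding only the EDSS main effect leaves the interaction bias in place (3.7 points at correlation 0.54).

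**8. Precision cost.** With error-free EDSS the interaction standard error grows by √[1/(1 − r²)], where r² = 0.21Δ²/(0.21Δ² + 2.25). For Δ = 1.5, 2 and 3, r² is 0.17, 0.27 and 0.46, so the factors are 1.10, 1.17 and 1.36. Simulation gives about 10%, 17% and 35%.

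**The case against.** Several objections carry weight.

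- *The wording is loose.* The sentence sits inside a power calculation. It says that EDSS is replaced, not that treatment*disability is removed, and section 9.2 does not rule out fitting both. That is fair, although removal of the interaction is the natural reading. If the interaction stayed, the model would hold treatment*EDSS without EDSS, which still does not adjust properly for disability. No section supplies a joint model.
- *Separate may mean tested in its own model.* If so, rewording the purpose is enough, and the remedy below allows for that. As written, the purpose reads as independence from disability.
- *Compare the two models.* They are not nested. If both show an interaction, neither says whether subtype adds anything beyond EDSS. Randomisation does not help, since neither characteristic is randomised.
- *The size rests on assumptions.* This stands in full. A rate of 23% needs 2 MFIS points of modification per EDSS point, so 2.5 EDSS points would amount to the whole 5-point design difference. At 0.5 point or less the false-positive rate is close to nominal. The simulations also pool the monotherapies and leave out the other covariates.
- *Adjustment is imperfect.* This also stands. EDSS is self-reported. Section 7.1.2 describes close agreement with clinician rating but gives no reliability. At an assumed reliability of 0.8 and 2 points of modification per EDSS point, the joint model still leaves about 1 point of false interaction for a 2-point gap and about 2 points for a 3-point gap.

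A reader might infer that any subtype effect this model finds must contain a disability effect, or that a false heterogeneity finding is likely. The documents do not support either. Both require a correlation and an EDSS effect that are not given, and a false interaction further requires that disability truly modifies response, which Aim 2 leaves open.

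**Conclusion.** The point holds as a mismatch between a model and its purpose: with no disability measure in it, the subtype model cannot say whether subtype matters apart from disability, whatever the size of the bias. That size is unknown. With 30% progressive, a 2-point EDSS gap and no true subtype effect, the false treatment*subtype rate runs from about 5-7% (0 to 0.5 MFIS point of modification per EDSS point) through about 10% (1 point) to about 23% (2 points).

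The reach is limited. This is a supplementary Aim 2 model. A reader might take the disability finding, or the trial's main result, to be compromised. Neither is: the EDSS modifier model stands on its own and the primary endpoint does not use the subtype model.

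**What to change.** In section 9.1, replace the substitution by an addition: fit MS subtype and treatment*subtype alongside self-report EDSS and treatment*EDSS, keeping both main effects and both interactions. State that the question of subtype apart from disability will be read only from this joint model, and that error in self-report EDSS may leave residual confounding. Carry the same specification into section 9.2, Aim 2. The subtype-only model may stay as an unadjusted description, without the claim of separation.

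No new data are needed: subtype is recorded in the baseline history (section 6.1) and self-report EDSS at baseline (section 6.9). The two extra terms, taking the model from 11 to 13 predictors, do not change the calculated power to three decimals. The real cost is the correlation. The subtype-interaction standard error is about 10-35% larger for EDSS gaps of 1.5-3 points. If EDSS shares 30% of the 0.04 increment, power is 94.1% (1 df) or 89.3% (2 df); if it shares 50%, 84.1% or 75.7%. The shared fractions are assumptions. The wider interval reflects what the data can show about two overlapping characteristics.

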To address these gaps in our knowledge, this pragmatic RCT will capitalize on a representative, heterogeneous sample of MS patients, novel patient-centered fatigue measures, and expertise from key stakeholders to compare the effectiveness of CBT monotherapy, modafinil monotherapy, and CBT+modafinil combination therapy on fatigue impact, fatigue severity, and fatigability in patients with MS (Aim 1), determine heterogeneity of treatment effects of common potential modifiers including depression, sleep disturbances, and MS disability level (Aim 2), and compare adverse events, treatment adherence, and patient dropout rates among the three treatments (Aim 3).

Objectives, Aims, Endpoints, and Assessments:

The Aims of this randomized, rater-blinded clinical trial are to: 1) Compare the effectiveness of 3 therapies: CBT monotherapy, modafinil monotherapy, and CBT+modafinil combination therapy on patient-reported fatigue impact, fatigue intensity, and fatigability among fatigued individuals with MS; 2) Test whether depression, sleep disturbances, or MS disability level modify comparative treatment responsiveness across treatment arms in terms of fatigue impact (i.e., heterogeneity of treatment effects); and 3) Compare adverse events, side effects, treatment adherence, and patient dropout rates among the three treatment arms and patient subgroups of interest.

Self-report measures of fatigue impact (Modified Fatigue Impact Scale - primary endpoint), fatigue intensity (Brief Fatigue Inventory) and potential effect modifiers (depression, sleep, and MS subtype/disability level) will be assessed at baseline, at 8-weeks, 12-weeks and 24 weeks. Subjects will also undergo 1 week of continuous actigraphy monitoring and EMA data collection with a wrist-worn accelerometer pre-treatment (baseline) and 12 weeks to collect additional data on physical activity level, fatigue intensity (numerical self-report scale), and fatigability (ratio of EMA fatigue intensity/physical activity level). **See Figure 1, study schematic, Section 3.** Hypotheses to be tested are that, at 12 weeks, treatment with combination therapy will overall lead to greater reductions in fatigue impact, fatigue severity, and fatigability compared to monotherapy, and that comorbid depression, sleep disturbances, and baseline disability level will be important effect modifiers that influence treatment effect and adherence.

Statistical Methods

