4. SUBJECT SELECTION

4.0 Subject Recruitment

Participants will be recruited from the UM and UW MS Clinics tertiary clinics. Additional participants will be recruited through UM and UW medical records; other neurology practices throughout Mid- and Southeastern Michigan (by invitation) and the Pacific Northwest, UM and UW electronic clinical trials registries; advertisement through community outlets (e.g., posting flyers in community centers, distributing flyers and fund raising walks), clinicaltrials.gov; Facebook and other social media campaigns, iConquerMS, and from advertisements posted by the NMSS (study stakeholder).

The table below shows the current enrollment plan for data collection.

Total number of study participants expected to be screened:	360
Of those screened, total number of study participants expected to be eligible:	340
Of those eligible, total number of study participants enrolled:	330
Target sample size (i.e., of those eligible, total number of study participants expected to be enrolled):	300 completers

We anticipate enrolling 50 subjects per site in year 1, 65 subjects per site in year 2, and 50 per site subjects in year 3, or an average of 4-5 subjects per month per site throughout the course of the study.

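### The Aim 1 model leaves out baseline depression, sleep and disability, forgoing a modest and nearly free gain in precision

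*Combined protocol and SAP*

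**What the plan says.** Section 9.2 (Aim 1) compares the change in MFIS from baseline to week 12 between arms with a repeated measures mixed model. It then says: "The mean difference will also be adjusted for baseline covariates: age, gender, anxiety, pain, and exercise". It justifies these five by their known association with fatigue or activity in MS.

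Other parts of the protocol treat three further baseline variables as related to fatigue:

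- Section 1.2 lists, among the gaps in earlier research, the lack of assessment of "common treatment effect modifiers associated with MS that contribute to fatigue (depression, sleep, and progressive MS/disability severity").
- The Section 3 schematic classes disability, sleep disorders and depression as effect modifiers. Demographics, anxiety, pain and exercise are classed as covariates.
- The Aim 2 model in Section 9.1 includes sleep disturbance, depression and EDSS as main effects and as interactions with treatment.
- The Aim 3 adherence model (Sections 9.1 and 9.2) adjusts for all three.
- The schedule in Section 6.9 collects the PHQ-8, the self-reported EDSS and several sleep scales at baseline.

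The Protocol Summary hypothesises that these variables "will be important effect modifiers that influence treatment effect and adherence".

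**The concern.** The stated reason for choosing covariates, association with fatigue, applies to depression, sleep and disability as well as to the five that were listed. The plan does not explain their absence from Aim 1.

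A baseline variable that predicts the outcome, when left out of the primary model, leaves its share of the variance in the residual. The confidence interval for the primary contrast is then wider than it need be, and any chance imbalance between arms on that variable passes into the estimate. The stake is efficiency and robustness, not validity. Baseline MFIS is also missing from the Aim 1 list, but that is a separate matter.

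**Working it through.** **Inputs from Section 9.1.** The comparison is "combined monotherapy groups vs. combination therapy, group weights 2:1", taken as 100 against 200. The test is specified "with a 2-sided alpha of 0.05 and standard deviation of 12". The claim is that "a sample size of n=300 subjects will provide 92% power to detect a delta-MFIS of 5".

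**Assumptions.** The plan does not say whether the SD of 12 is raw or residual; here it is taken as the residual SD after the five planned covariates. The plan gives no R-square for the three variables alone. The only figure, "assuming the R-squared explained by the adjustment variables is at least 0.3", refers in Aim 2 to a whole adjustment set that also contains baseline fatigue. The joint partial R-square (R²) of the three is therefore varied from 0 to 0.20.

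**1. Reproduce the stated power.** SE = 12 × √(1/100 + 1/200) = 1.470. Then 5/1.470 = 3.402, and Φ(3.402 − 1.96) = 92.5%. The noncentral t with 298 df gives 92.4%. The stated 92% is confirmed.

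**2. Charge for the covariates.** With k baseline covariates, error df = 298 − k. The variance is inflated by (300 − 3)/(300 − 3 − k) to allow for chance imbalance.

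- Planned model, k = 5: SE = 1.470 × √(297/292) = 1.482; noncentrality 5/1.482 = 3.373; 293 df; power 92.0%.
- Three added, k = 8: SE = 1.470 × √(297/289) × √(1 − R²); 290 df.

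| Joint partial R² (assumed) | SE | Power |
|---|---|---|
| 0 | 1.490 | 91.7% |
| 0.01 | 1.482 | 92.0% |
| 0.02 | 1.475 | 92.2% |
| 0.05 | 1.452 | 93.0% |
| 0.10 | 1.413 | 94.1% |
| 0.20 | 1.333 | 96.2% |

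With a critical value of 1.968, the 95% half-width is 1.968 × 1.482 = 2.92 MFIS points as planned. It becomes 2.86 at R² = 0.05 and 2.78 at R² = 0.10.

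**3. Break-even.** The two variances are equal when 1 − R² = 289/292, so R² = 3/292 = 1.0%. If sleep or disability needed two further terms (k = 10), break-even is 1 − 287/292 = 1.7%, and the worst-case loss is 0.4 points instead of 0.3.

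**4. Simulation check (8,000 trials per scenario).** Without and with the three covariates, power is 92.0% and 91.6% at R² = 0, 91.7% and 92.7% at 0.05, and 91.9% and 94.1% at 0.10. Type I error is about 5% in every case, with or without them.

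**5. Chance imbalance.** The standardised imbalance between groups has SE √(1/100 + 1/200) = 0.122, so a 1.96-SE imbalance is 0.24 SD. The contrast shifts by √R² × 12 × 0.24, which is 0.4, 0.6 or 0.9 MFIS points at R² = 0.02, 0.05 or 0.10, against a design difference of 5.

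**6. If missing covariates removed participants.** With R² = 0 and complete-case analysis, losing 2%, 5% or 10% of participants gives power of 91.2%, 90.3% or 88.6%. Break-even R² rises to about 3%, 6% or 11%. The loss rates are assumptions; Section 6.6 says only that skipped questions are rare.

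**The case against.** **The split of roles is deliberate.** Section 3 separates effect modifiers from covariates, and the Aim 1 list follows that split. A model containing the three variables is already planned for Aim 2. This is fair: the omission may be a choice and not an oversight. But a modifier can also be a main effect, the Aim 2 model treats these variables that way, and the plan gives no reason for keeping them out of Aim 1.

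**The gain is small and assumed.** This stands. Section 1.2 links the variables to fatigue, not to change in MFIS. Nothing in the plan shows what they add beyond anxiety and pain.

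**The fix needs definitions the plan lacks.** This also stands. Sleep disturbance (yes/no) has no single rule across the STOP-Bang, Insomnia Severity Index and RLS index. Depression is the PHQ-9 in Section 9.1 but the PHQ-8 in the schedule and in the Aim 3 text of Section 9.2. Sections 6.1 and 6.3 also disagree on whether the baseline surveys come before randomisation, which affects the anxiety, pain and exercise covariates equally.

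A reader might infer three stronger claims. The documents support none of them.

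- *That the protocol says these variables drive adherence, and hence that omitting them undermines the handling of missing data.* The adherence link is a hypothesis to be tested, and no link to dropout is stated. Section 4.0 plans 330 enrolled for "300 completers" without relating loss to these variables. The repeated measures model may also draw on week-8 and week-24 scores. If the variables did predict dropout, including them would make a missing-at-random assumption more plausible, but that is conditional.
- *That the word* also *in Section 9.2 creates two rival primary estimates and inflates type I error.* The section describes one model and then its covariates. An unadjusted power calculation does not create a second primary test. The wording merits clarification, but no error-rate figure follows from it.
- *That the omission biases the result or makes the power claim wrong.* Randomisation protects the contrast when data are complete, and the power reproduces.

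**Conclusion.** The point holds as a modest matter of efficiency and clarity. By the plan's own criterion, baseline depression, sleep and disability belong beside the five listed covariates. Adding them moves power from 92.0% to about 93.0% to 94.1% if their joint partial R² is 0.05 to 0.10, and costs about 0.3 points if they predict nothing.

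These figures rest on an SD of 12 taken as residual, complete baseline data, the pooled 200 against 100 contrast, and an R² that the documents do not supply. The addition is nearly free, not unconditionally so: the variables must explain about 1% of the remaining variance to pay for themselves, and more if missing values remove participants.

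**What to change.** In Section 9.2, Aim 1:

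- Add as baseline main effects the PHQ-8 score, one named sleep score (for example the Insomnia Severity Index total, in place of the undefined yes/no indicator) and the self-reported EDSS.
- State that participants with missing baseline covariate values stay in the analysis, for example by simple imputation from baseline data.
- State that the covariate-adjusted week-12 contrast is the primary estimate and the unadjusted difference is supportive.
- Reconcile Sections 6.1 and 6.3 so that every adjustment covariate is measured before randomisation.

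If the three variables are meant only for Aim 2, one sentence giving the reason would settle the covariate question. The full change costs a few sentences and three degrees of freedom (293 to 290), and needs no new data.

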Aim 3: Compare adverse events, side effects, treatment adherence, and patient dropout rates among the three treatment arms and patient subgroups of interest. Descriptive statistics will be used to analyze patterns of adverse events including side effects (incidence, type, severity, and relatedness) and treatment adherence between treatment groups (modafinil vs. CBT vs. combination therapy) throughout the 12-week intervention interval. Adverse event frequency between treatment groups and among subgroups of interest will be evaluated using ANOVA. Multiple linear regression models adjusted for age, gender, EDSS score, baseline fatigue level, baseline activity level, presence of sleep disorder (yes/no), and depression severity (PHQ-8 Score) will be used to determine association between treatment group and treatment adherence (percent usage of prescribed therapy). We also will assess whether degree of treatment effects measured in Aim 1 are related to treatment adherence (e.g. “dose response”).

9.3 Analysis of Exploratory Aims:

Additional analyses modeled as in 9.2 above will also evaluate treatment effect on the difference between 8 week and baseline MFIS scores, to assess whether treatment effects are detectable prior to the 12-week assessment period.

Additional analyses modeled as in 9.2 above will also evaluate treatment effect on the difference between 24 week and baseline MFIS scores, to assess whether treatment effects are detectable following the 12-week assessment period.

Descriptive statistics will be used to summarize clinical treatment utilization patterns between 12-24 weeks, following the 12-week intervention interval.

Analyses modeled as in 9.2 will also be used to evaluate treatment effects on other outcomes at 12 and 24 weeks. We will examine differential treatment effects on changes in the following

factors (assessed via survey): ability to participate in social roles and activities, pain interference, quality of life, and self-efficacy for managing MS symptoms. We will also examine differential treatment effects on changes from baseline to 12 and 24 weeks in the following outcomes that were assessed via survey and/or EMA: pain intensity, perceived cognitive functioning, and pacing behaviors. Treatment group differences in scores on the PGIC measure at 12 and 24 weeks will be examined in models similar to the approach described in 9.2.

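### The Aim 3 adherence model is additive, so no specified analysis can show whether the arm difference in adherence varies with depression, sleep or disability

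*Combined protocol and SAP*

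**What the plan says.** The Protocol Summary (Objectives, Aims, Endpoints, and Assessments) puts adherence beside treatment effect in one hypothesis: "comorbid depression, sleep disturbances, and baseline disability level will be important effect modifiers that influence treatment effect and adherence". Aim 3 in section 9.2 is to "Compare adverse events, side effects, treatment adherence, and patient dropout rates among the three treatment arms and patient subgroups of interest".

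The analysis given for adherence is multiple linear regression, adjusted for age, gender, EDSS, fatigue and activity at baseline, sleep disorder and depression. The end of that sentence gives its purpose: "presence of sleep disorder (yes/no), and depression severity (PHQ-8 Score) will be used to determine association between treatment group and treatment adherence". The matching power statement in section 9.1 assumes "a full model consisting of up to 8 possible predictor variables: treatment group (independent variable of interest"), followed by seven covariates. For 300 participants it concludes: "we will have 95% power to detect an R-square difference of 0.03 for the test predictor of interest". The covariates are taken to account for an R-squared of 0.3 or more.

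Interactions of treatment with sleep, depression and disability are written out in section 9.1 for Aim 2 only, where the dependent variables are fatigue outcomes.

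**The concern.** The hypothesis uses the language of effect modification for adherence, but the model that is meant to serve it contains the modifiers only as additive covariates. The terms that would test modification appear for fatigue and are absent for adherence.

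What is at stake is treatment choice. The clinical rationale in section 1.2 asks which patient characteristics should steer a patient towards CBT or modafinil. If, say, depressed participants missed CBT sessions but took their tablets, that would bear directly on the question. An additive model would report one depression coefficient, averaged over the arms. Interactions chosen after the data are seen would be post hoc.

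**Working it through.** **1. Is there an analysis that addresses differential adherence?** Taking the places where one could be specified:

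- Section 9.1, Aim 3: eight predictors, none a product term.
- Section 9.2, Aim 3 regression: the same variables, aimed at the treatment-group association.
- Section 9.2, Aim 3 descriptive statistics: adherence by treatment group. Subgroups are attached only to the ANOVA of adverse event frequency.
- Section 9.2, Aim 2 interactions: fatigue impact, intensity and fatigability; adherence is not listed.
- Section 9.3: no analysis of adherence by subgroup.

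**2. What the additive model can estimate.** Write expected adherence as a + b(arm) + d × depression + other covariates. The CBT-minus-modafinil difference is b(CBT) − b(modafinil) at every value of depression. The coefficient d does show whether adherence falls with depression overall. With a product term the difference becomes b(CBT) − b(modafinil) + [g(CBT) − g(modafinil)] × depression. The bracket is the modification, and the stated model fixes it at zero.

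**3. The plan's own power figure.** For a partial F-test, f² = ΔR² / (1 − R² of the full model), noncentrality λ = n × f², and denominator df = n − p − 1. Inputs from section 9.1: n = 300, ΔR² = 0.03, adjustment R² = 0.3. Alpha 0.05 is stated there for Aim 1 and assumed to carry over.

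- f² = 0.03 / (1 − 0.33) = 0.0448; λ = 300 × 0.0448 = 13.4.
- Treatment on 1 df, p = 8, denominator df 291: power 95.5%. The stated 95% reproduces.
- Treatment on 2 df (three arms), p = 9, denominator df 290: power 91.4%.

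The stated figure therefore matches a 1-df treatment term. It does not itself prove the model additive, because a 1-df test with p = 11 also gives 95.5%. The evidence for additivity is the predictor list.

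**4. Power with the interactions added.** Treatment takes 2 df, the seven covariates 7, and three interactions 2 df each: p = 2 + 7 + 6 = 15, denominator df 284. The documents give no interaction effect size for adherence, so ΔR² is an assumed range. The other terms are taken to explain 0.3, as in section 9.1.

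| Assumed ΔR² | λ | One 2-df interaction | Bonferroni over three | Joint 6-df test |
|---|---|---|---|---|
| 0.03 | 300 × 0.03/0.67 = 13.4 | 91% | 83% | 78% |
| 0.02 | 300 × 0.02/0.68 = 8.8 | 76% | 60% | 57% |
| 0.01 | 300 × 0.01/0.69 = 4.3 | 44% | 28% | 29% |

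If the other terms explained only 0.1, the single-interaction figures would be 83%, 64% and 35%.

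**5. How far the common coefficient could mislead (all inputs assumed).** Suppose depressed participants fall short by 20 points on CBT and 0 on modafinil, with equal arms and equal prevalence. The common coefficient is (20 + 0 + c)/3, where c is the shortfall in the combination arm: 6.7, 10 or 13.3 points for c = 0, 10 or 20.

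**6. Dropout.** Section 4.0 plans 330 enrolled and 300 completers, so about 30 dropouts. A logistic model with the same 15 parameters has 30/15 = 2 events per parameter.

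**The case against.** The strongest reply is that the Summary sentence may mean only that these factors predict adherence. The numbered aims fit that reading: Aim 2 confines modification to fatigue outcomes, and Aim 3 can be read as comparing arms and, separately, comparing subgroups. The regression includes EDSS, sleep disorder and PHQ-8, so it estimates both. This softens the mismatch. It does not remove it, because the sentence calls the factors effect modifiers and the regression's declared target is the treatment-group association alone.

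A second reply is that section 9.2 speaks of regression models in the plural, so interactions are not excluded. That is correct, but none is specified.

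A third is that modest modification would often be missed. That stands, and it limits the remedy to estimation. It also stands that adherence is the share of prescribed therapy used, which means sessions in one arm, tablets in another and both in the third, with no stated rule for combining them. An arm-by-depression term needs that caveat.

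A reader might infer that the plan can say nothing about adherence in subgroups, or that its coefficients are wrong for every arm. The documents support neither. Overall subgroup differences are estimable, and the common coefficient misleads only if a sizeable interaction exists, which the documents neither show nor quantify.

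**Conclusion.** The concern holds as a gap between a stated hypothesis and the specified analysis: nothing in sections 9.1 to 9.3 can show whether the arm difference in adherence varies with depression, sleep or disability. Aim 3's 95% power figure reproduces with a 1-df treatment term and is not in dispute. The primary and secondary endpoints are unaffected.

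Its size can be given only conditionally. At n = 300, a 2-df interaction has good power (91%) at the increment the plan uses for its Aim 3 treatment effect. Power is 76% at an increment of 0.02 and 44% at 0.01, before multiplicity. These figures rest on an assumed adjustment R-squared of 0.3 and on assumed increments. The 6.7 to 13.3 point illustration shows the mechanism and does not predict a result.

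Because Aim 3 also covers dropout, a reader might infer that dropout needs the same interaction model. The planned numbers do not support that.

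**What to change.** - Keep the additive regression for the overall arm comparison, with treatment as a 2-df factor.
- Pre-specify a secondary adherence model that adds treatment-by-depression, treatment-by-sleep-disorder and treatment-by-EDSS terms, using baseline values (scores centred). State that they are fixed effects, since the Summary treats the Aim 2 interactions as random.
- Report the depression, sleep and disability effects by arm with confidence intervals, labelled exploratory, and say that a null result does not rule out modification.
- Report dropout descriptively by arm and subgroup.
- Alternatively, if only prediction was meant, narrow the Summary hypothesis to say that these factors predict adherence.

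The cost is analysis-plan wording and a little programming. The schedule in section 6.9 already collects EDSS, PHQ-8 and the sleep-disorder instruments at baseline, and adherence at weeks 8 and 12. The downside is six more parameters in a model of about 300 participants, and limited power for modest modification.
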